4.4.2 Antiemetics

The use of antiemetics will be left to the investigators' discretion.

4.4.3 Palliative Care

Palliative radiation and surgery are allowed on this trial IF they are not being used to address a target lesion as defined in RECIST 1.1. Any patient who requires palliative care to a target lesion should be removed from protocol treatment. If necessary, the following parameters should be used.

- Palliative radiation: Protocol treatment should be held 7 days before, during, and 7 days after palliative radiation, or at the discretion of the site radiation oncologist. If treatment is not resumed within 3 weeks, case will be reviewed by QAM and PI to determine whether or not patient can restart treatment.
- Palliative surgery: Protocol treatment should be held 7 days before and until the wound is healed. If treatment is not resumed within 3 weeks, case will be

reviewed by QAM and PI to determine whether or not patient can restart treatment.

4.4.4 **OTHER Concomitant Medications**

Therapies considered necessary for the well-being of the patient may be given at the discretion of the investigator. Other concomitant medications should be avoided except for analgesics, chronic treatments for concomitant medical conditions, or agents required for life-threatening medical problems. All concomitant medications must be recorded. For patients with known hypertension on BP medications, strict compliance with treatment should be reinforced.

4.4.5 **Concomitant Medications discouraged while on study**

- Strong inducers and inhibitors of CYP450 listed in Appendix A
- CYP3A4 substrates can be administered, but investigators will need to be aware of possible increased or decreased effectiveness of the non-study drug and this should be recorded in concomitant medications.
- BCRP and PgP inducers and inhibitors should be used with caution if another alternative drug is not able to be used (listed in the Appendix B).
 - *Note: As this list is constantly evolving, if a medication is incorrectly documented as prohibited in this protocol, documentation from the site pharmacist to the contrary will be acceptable*
- Other Anticancer or Experimental Therapies: No other anticancer therapy (including chemotherapy, radiation, hormonal treatment or immunotherapy) of any kind is permitted during the study period. No other drug under investigation may be used concomitantly with the study drug.

4.5 **Duration of Therapy**

If a patient is felt to be deriving benefit from the agents and is stable at the conclusion of the trial, patients are allowed to continue therapy with stable disease by RECIST 1.1. This will be based on discussion with the patient, the PI, and sponsor. It may be possible to continue both drugs at that point, assuming availability of agents and no change in the status regarding pazopanib or topotecan with respect to sarcomas.

A patient may be removed from therapy if, in the judgment of the investigator, general or specific changes in the patient's condition render the patient unacceptable for further treatment.

4.6 **Duration of Follow Up**

Patients with PD at end of treatment will be followed every 6 months for 2 years (or until death) for survival. Patients without PD at end of treatment will be followed every 6 months for 5 years (or until death) for survival and progression. Follow-up may occur over the phone. Patients who are removed from study treatment for toxicity should be followed until toxicity resolves to grade 1 or baseline.

4.7 **Removal of Subjects from Study Treatment and/or Study as a Whole**

Patients can be taken off the study treatment and/or study as a whole at any time at their own request, or they may be withdrawn at the discretion of the investigator for safety, behavioral or administrative reasons. The reason(s) for discontinuation must be clearly documented on the appropriate eCRF and may include:

- Patient voluntarily withdraws from treatment (follow-up permitted)
- Patient withdraws consent (no follow-up permitted)
- Patient is unable to comply with protocol requirements

- Patient demonstrates disease progression
- Patient experiences unacceptable toxicity
- Treating physician determines that continuation on the study would not be in the patient's best interest
- Patient becomes pregnant
- Patient develops a second malignancy that requires treatment which would interfere with this study
- Patient becomes lost to follow-up (LTF)

4.8 Patient Replacement

If a patient is registered but withdraws or is taken off treatment before receiving any doses of study medication, he or she will then be replaced.

- a. Pre-study procedures done within 7 days of C1D1 do not need to be repeated on C1D1.
- b. Pre-study H&P and all labs must be < 15 days before registration. Tumor measurements and radiologic evaluations must be ≤ 4 weeks before registration. Screening EKG must be within 28 days prior to registration. H&P and all labs do not need to be repeated on day 1 if done within 7 days of treatment initiation.
- c. Vital signs to include height (height is recorded at screen visit only), weight, blood pressure, pulse, temperature and respirations. In addition to this full set of vitals each cycle, a measurement of blood pressure (BP) should be taken every 7 days (+/- 3). These weekly blood pressure measurements can be assessed by any method (i.e. at home or by another physician) as long as the study physician is informed of the measurement, verifies any measurement that is not normal and takes appropriate action to manage hypertension, as defined by the protocol. A blood pressure log will be maintained to aid in monitoring and should be uploaded into NOTIS each cycle for the duration of treatment (See appendices).
- d. EKG: Performed on Cycle 2 day 1 and then day 1 of every even cycle until end of treatment (+/-3 days). EKG for screening must be within 28 days prior to registration.
- e. Thyroid function test (TSH) are monitored every 12 weeks (+/-3 days). TSH is mandatory, but T4 should be restricted to only those with abnormal TSH levels.
- f. Chemistry labs include a comprehensive chemistry panel (Liver function tests (LFT) and Comprehensive Metabolic Panel (CMP)). Monitoring of LFTs: Monitor serum liver tests before initiation of treatment with pazopanib and at Cycle 1 day 15, Cycle 2 day 1, Cycle 2 day 15, and day 1 of every cycle thereafter (+/- 3 days). CMP and LFTs should include: Bilirubin, Glucose, BUN, Calcium, Total Protein, Albumin, ALT, AST, GFR, Sodium, Potassium, Chloride, Carbon Dioxide, Alk Phos, Creatinine, Magnesium, and GGT.
- g. Only for women of childbearing potential; must be tested within 7 days prior to registration.
- h. Complete Blood Count (CBC): Performed on day 1 and 15 of cycles 1 and 2 (+/- 3 days) then day 1 of each cycle (+/-3 days). For patients experiencing significant cytopenias felt possibly related to Topotecan, CBCs should be obtained more frequently (weekly or more frequently) to assess timing for retreatment or need for G-CSF or transfusion support.
- i. Patients **with PD** at end of treatment will be followed every 6 months for 2 years (or until death) for survival (from the last day of treatment). Patients **without PD** at end of treatment will be followed every 6 months for 5 years (or until death) for survival and progression (from the last day of treatment). Follow-up may occur over the phone.
- j. Patients who are removed from study treatment for toxicity should be followed until toxicity resolves to grade 1 or baseline.
- k. Radiology assessment by CT or MRI will be done at Week 6, Week 12, Week 20 and every 8 weeks (+/- 7 days) thereafter. After 1 year of protocol treatment, patient may be switched to scans every 12 weeks (+/- 7 days) at the discretion of the patient and treating physician.
- l. Blood samples for mandatory correlative study will be collected at screening or on Cycle 1 Day 1 prior to treatment, and day 1 of Cycle 2, 3, and 4 , (+/-3 days) as in section 9.1.
- m. Unless otherwise noted, on-therapy windows for testing will be as follows: imaging scans should be completed within +/- 1 week of the target time point, and labs and physical examinations within +/- 3 days of the target time point.
- n. End of treatment visit must occur within 30 days following the last day of treatment, particularly prior to patient starting new treatment.
- o. Patient to call coordinator weekly to report toxicities- if no toxicities to be reported, patient need not call in. Toxicities should be followed for 30 days after last dose of study treatment, however, new toxicities that arise within the 30 day period definitely related to new anti-cancer treatment and NOT related to study treatment do not need to be reported.
- p. ONLY required for patients with prior anthracycline use OR otherwise at risk for left ventricular systolic dysfunction. May be assessed by MUGA or echocardiogram.
- q. Day 1 of each cycle should be every 28 days. In the event that this day falls on a holiday or other such event, study team should use +/- 3 day window to complete pre-treatment procedures, and dispense protocol agents to patients with instructions to commence treatment on day 1. Any missed doses will not be made up and should be skipped to maintain a 28-day cycle.

6.0 ENDPOINT ASSESSMENT

6.1 Definitions

6.1.1 Measurable Disease

Measurable lesions are defined as those that can be accurately measured in at least one dimension (longest diameter to be recorded) as >20 mm with conventional techniques (CT, MRI, x-ray) or as >10 mm with spiral CT scan. All tumor measurements must be recorded in millimeters (or decimal fractions of centimeters). Lymph nodes are considered measurable in RECIST 1.1 if their short diameter exceeds 15 mm. Lymph nodes are considered normal if they have a short axis of less than 10 mm; this applies to determination of response as well. Lesions that are previously irradiated must show clear evidence of progression over a minimum of 3 months to include as measurable. This period of time is used to discount tumor edema in an irradiated field as a false sign of disease progression.

6.1.2 Non Measurable Disease

All other lesions (or sites of disease), including small lesions (longest diameter <20 mm with conventional techniques or <10 mm using spiral CT scan), are considered non-measurable disease. Bone lesions, leptomeningeal disease, ascites, pleural/pericardial effusions, lymphangitis cutis/pulmonis, inflammatory breast disease, abdominal masses (specifically abdominal masses not followed by CT or MRI), and cystic lesions are all non-measurable.

6.1.3 Target Lesions

All measurable lesions up to a maximum of 2 lesions per organ and 5 lesions in total, representative of all involved organs, should be identified as target lesions and recorded and measured at baseline. Target lesions should be selected on the basis of their size (lesions with the longest diameter) and their suitability for accurate repeated measurements (either by imaging techniques or clinically). A sum of the longest diameter (LD) for all target lesions will be calculated and reported as the baseline sum LD. The baseline sum LD will be used as reference by which to characterize the objective tumor response

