6.1.3.1 Evaluation of Target Lesions

Complete Response (CR)

Disappearance of all target lesion

Partial response (PR)

At least a 30% decrease in the sum of the longest diameter (LD) of target lesions, taking as reference the baseline sum LD

Progressive Disease (PD)

At least a 20% increase in the sum of the LD of target lesions, taking as reference the smallest sum LD recorded since the treatment started or the appearance of one or more new lesions. Progression must also involve an increase in size of measurable lesions by at least 5 mm, to minimize the possibility that small changes in a small number of target lesions is falsely interpreted as progression.

Stable Disease (SD)

Neither sufficient shrinkage to qualify for PR nor sufficient increase to qualify for PD, taking as reference the smallest sum LD since the treatment started.

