6.2 Antitumor Effect

For the purposes of this study, patients should be re-evaluated for response at 6 weeks, 12 weeks and then every 2 cycles thereafter. In addition to a baseline scan, confirmatory scans should also be obtained a minimum of 4 weeks following initial documentation of objective response. The investigator may opt to have the follow up scan performed according to the schedule (without an extra scan) as this follows the intent of the RECIST guidelines.

Response and progression will be evaluated in this study using the Response Evaluation Criteria in Solid Tumors (RECIST) Committee, version 1.1.64 Changes in only the largest diameter (unidimensional measurement) of the tumor lesions are used in the RECIST criteria, as defined below. In contrast, measurable disease in lymph nodes is determined based on the lymph node short axis.

6.3 Valuable for objective response:

All patients enrolled in the study should be assessed for response to treatment, even if there are major protocol treatment deviations or patients exhibit objective disease progression prior to the end of cycle 1.

All conclusions should be based on all enrolled patients. Subanalyses may then be performed on the basis of a subset of patients, excluding those for whom major protocol deviations have been identified (e.g., early death due to other reasons, early discontinuation of treatment, treating an ineligible patient, major protocol violations, etc.). However, these subanalyses may not serve as the basis for drawing conclusions concerning treatment efficacy, and the reasons for excluding patients from the analysis should be clearly reported. The 95% confidence intervals for response rate should also be provided.

All patients who were enrolled on the trial should be included in the main analysis of the response rate. Thus, an incorrect treatment schedule or drug administration does not result in exclusion. However, if a patient is removed from treatment prior to their 12 week assessment for reasons other than disease progression or death, they will be considered non-evaluable for response if approved by the DMC.

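### Followed literally, 6.1.3 and 6.1.3.1 deny CR to a target node that 6.1.1 calls normal, and let its longest diameter trigger progression while it stays normal

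*Combined protocol and SAP*

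**What the plan says.** Four places in section 6 bear on nodal target lesions.

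- **6.1.1 (Measurable Disease)** admits nodes by short axis: "Lymph nodes are considered measurable in RECIST 1.1 if their short diameter exceeds 15 mm". It then sets a normal size and carries it into response: "Lymph nodes are considered normal if they have a short axis of less than 10 mm; this applies to determination of response as well". For measurable lesions in general, the dimension it asks sites to record is the longest diameter.
- **6.1.3 (Target Lesions)** draws targets from "All measurable lesions up to a maximum of 2 lesions per organ and 5 lesions in total", which does not exclude nodes. It then says: "A sum of the longest diameter (LD) for all target lesions will be calculated and reported as the baseline sum LD".
- **6.1.3.1 (Evaluation of Target Lesions)** defines CR as "Disappearance of all target lesion", PR as "At least a 30% decrease in the sum of the longest diameter (LD) of target lesions" from baseline, and PD as "At least a 20% increase in the sum of the LD of target lesions" from the smallest sum, with an absolute increase of at least 5 mm. It has no nodal exception.
- **6.2 (Antitumor Effect)** names RECIST 1.1, says that change is judged on the largest diameter only, and adds: "In contrast, measurable disease in lymph nodes is determined based on the lymph node short axis". It does not say which nodal dimension goes into the sum.

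**The concern.** Short axis decides whether a node can be a target and when it is normal again, but longest diameter decides what it contributes to every response and progression call. The two rules conflict once a target node falls below 10 mm short axis. From then on 6.1.1 regards it as normal for response, while 6.1.3.1 still requires it to vanish before CR can be called and still counts its full length toward progression.

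Target-sum progression is one component of the primary 12-week progression-free endpoint (2.1, 6.5), and CR plus PR is a secondary endpoint (2.2.1, 6.6). A literal reading could therefore record a progression in a node that 6.1.1 calls normal, or withhold a response from a patient whose only target has normalised.

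**Working it through.** The plan gives no figure on this point to reproduce. The check applies the plan's own rules to nodal measurements. The node sizes are assumptions chosen to show the mechanism, because the documents contain none. Each example has one target node, no non-target disease and no new lesions, and leaves the confirmation scan aside.

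**Rules used**, with S the sum of longest diameters in mm:
- PR: (S_baseline − S_now) / S_baseline ≥ 30%.
- PD: (S_now − S_smallest) / S_smallest ≥ 20%, and S_now − S_smallest ≥ 5 mm.
- CR: the target has disappeared (6.1.3.1).
- Normal node: short axis < 10 mm, also for response (6.1.1).
- Eligible as a nodal target: short axis > 15 mm (6.1.1). The 18 mm baseline short axis below qualifies.

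**Example 1: the node normalises, then lengthens while still normal.**

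| Scan | Longest x short axis | Change in S | Call by 6.1.3.1 | Status by 6.1.1 |
|---|---|---|---|---|
| Baseline | 28x18 | – | – | measurable |
| Second | 15x7 | (15 − 28)/28 = −46.4% | PR; not CR, because the node is still present | normal (7 mm) |
| Third | 21x9 | (21 − 15)/15 = +40%; 21 − 15 = +6 mm | PD | still normal (9 mm) |

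The short axis grew by only 9 − 7 = 2 mm, which is below the 5 mm minimum. Scans are scheduled at weeks 6 and 12 (study procedures, footnote k). If the second and third scans were those two, the patient would be a failure on the primary endpoint.

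**Example 2: the node normalises with a modest change in length.** It goes from 28x18 to 22x9. The longest diameter changes by (22 − 28)/28 = −21.4%, short of 30%, so 6.1.3.1 gives SD. The short axis changes by (9 − 18)/18 = −50% and is now below 10 mm, which 6.1.1 calls normal for response. The patient is not counted in ORR.

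**What each example can move.** Example 1 at the third scan can change the 12-week rate. Example 1 at the second scan cannot change ORR, because a CR recorded as PR is still a responder. Example 2 can change ORR but not the clinical benefit rate, which already includes SD.

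**Scale.** Each patient reclassified on the primary endpoint moves the rate by 1/92 = 1.1 percentage points. If between 0 and 3 evaluable patients were affected (an assumption), the range is 0 to 3/92 = 3.3 points, against the 11-point difference the trial is designed to detect.

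**The case against.** The strongest reply is that the plan prescribes only one sum. Sections 6.1.3 and 6.1.3.1 consistently say longest diameter, and the PD rule read alone is clear. 6.1.1 covers measurability and normality, and the nodal sentence in 6.2 covers measurability. This is correct, and it limits the point. A reader might infer that two sites would calculate different sums for any patient with a nodal target. For example, a sole node going from 30x16 to 32x22 is +6.7% by longest diameter and +37.5% (+6 mm) by short axis. That node never falls below 10 mm, so 6.1.1's normality rule does not apply, and the comparison is with a short-axis sum that no section prescribes. The conflict within the documents is confined to nodes that have normalised.

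A second reply is that naming RECIST 1.1 settles the matter. The plan also writes out its own rules, and those apply longest diameter to every target. A general reference does not tell a site to set explicit text aside.

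A third is that 6.1.1 is itself the nodal exception to the CR rule. It can be read so, and it would then be too strong to say that CR is impossible for these patients. But 6.1.3.1 does not refer back to it, and that reading still leaves the PD rule unmodified.

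A reader might also infer that the trial's conclusion hinges on a single nodal call, for instance 56 against 57 progression-free patients. Both counts meet the stated cut-off of 56 or more of 92, so the decision is the same. The error rate attached to that cut-off is a separate issue.

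**Conclusion.** The inconsistency is real, and its core needs no outside source. For a target node below 10 mm short axis, 6.1.1 says normal for response. 6.1.3.1, followed literally, says not CR, and can say PD if the node lengthens by at least 20% and 5 mm from the smallest sum. A node that normalises with less than a 30% fall in length is SD rather than a response.

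The reach is limited to patients with nodal targets, and the documents do not say how many there are. The effect on the 12-week rate and on ORR is therefore unknown in size. The examples show that misclassification is possible, not that it occurred. Section 6 should be corrected, but the documents give no ground for saying the trial's conclusion would change.

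**What to change.** In 6.1.3, 6.1.3.1 and 6.2, state that non-nodal targets contribute longest diameter and nodal targets contribute short axis to one sum, and that PR, SD and PD are all judged on that sum. In the CR definition, state that a nodal target counts as resolved when its short axis is below 10 mm, as 6.1.1 already says.

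Cohort 1 is closed to accrual (Appendix H, Amendment 10) and has passed its interim analysis. Replacing its calls now would be a post hoc change to the primary endpoint. For enrolled patients with nodal targets, re-derive the 12-week progression-free rate and ORR under the clarified rule and report both as a sensitivity analysis, where short axes were recorded. State how many patients have nodal targets and how many calls change.

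The cost is a few sentences plus a re-derivation for the affected patients. The downside is that 6.1.1 asks only for the longest diameter to be recorded, so some short axes may be missing and the re-derivation may be incomplete. The report should say how many could not be re-derived.

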6.1.3.1 Evaluation of Target Lesions

Complete Response (CR)

Disappearance of all target lesion

Partial response (PR)

At least a 30% decrease in the sum of the longest diameter (LD) of target lesions, taking as reference the baseline sum LD

Progressive Disease (PD)

At least a 20% increase in the sum of the LD of target lesions, taking as reference the smallest sum LD recorded since the treatment started or the appearance of one or more new lesions. Progression must also involve an increase in size of measurable lesions by at least 5 mm, to minimize the possibility that small changes in a small number of target lesions is falsely interpreted as progression.

Stable Disease (SD)

Neither sufficient shrinkage to qualify for PR nor sufficient increase to qualify for PD, taking as reference the smallest sum LD since the treatment started.

6.1.4 Non-Target Lesions

All other lesions (or sites of disease) including any measurable lesions over and above the 10 target lesions should be identified as non-target lesions and should also be recorded at baseline. Measurements of these lesions are not required, but the presence or absence of each should be noted throughout follow-up.

6.1.4.1 Evaluation of Non-Target Lesions

Complete Response (CR)

Disappearance of all non-target lesions

Note: If tumor markers are initially above the upper normal limit, they must normalize

for a patient to be considered in complete clinical response.

Incomplete Response/Stable Disease (SD)

Persistence of one or more non-target lesion(s) and/or maintenance of tumor marker level above the normal limits.

Progressive Disease (PD)

Appearance of one or more new lesions and/or unequivocal progression of existing non-target lesions. Please refer to the RECIST 1.1 guidelines for a discussion of “unequivocal progression”.

Although a clear progression of “non-target” lesions only is exceptional, the opinion of the treating physician should prevail in such circumstances, and the progression status should be confirmed at a later time by the review panel (or Principal Investigator).

Evaluation of Best Overall Response

The best overall response is the best response recorded from the start of the treatment until disease progression/recurrence (taking as reference for progressive disease the smallest measurements recorded since the treatment started). The patient's best response assignment will depend on the achievement of both measurement and confirmation criteria. Since this is not a randomized study, confirmation of a clinical response is required as per RECIST 1.1; it is not required for randomized studies in RECIST 1.1.

| Target Lesions | Non-Target Lesions | New Lesions | Overall Response | Best Response for this Category Also Requires: |
|---|---------------------------|--------------------|-------------------------|---|
| CR | CR | No | CR | ≥4 week Confirmation |
| CR | Non-CR/Non-PD | No | PR | ≥4 week Confirmation |
| PR | Non-PD | No | PR | |
| SD | Non-PD | No | SD | documented at least once ≥4 week from baseline |
| PD | Any | Yes or No | PD | no prior SD, PR or CR |
| Any | PD* | Yes or No | PD | |
| Any | Any | Yes | PD | |
| * In exceptional circumstances, unequivocal progression in non-target lesions may be accepted as disease progression. | | | | |

Note: Patients with a global deterioration of health status requiring discontinuation of treatment without objective evidence of disease progression at that time should be reported as “*symptomatic deterioration*”. Every effort should be made to document the objective progression even after discontinuation of treatment.

